## **B. Background and Significance**

An estimated 1.6 to 3.8 million sport-related traumatic brain injuries occur annually in the United States, the vast majority being concussions. Despite this high prevalence, the clinical management of concussion remains difficult. Recovery of symptoms following a concussion usually occurs within a few days to a few weeks of injury. These symptoms, which include cognitive difficulties, headache, and dizziness, are pervasive, impacting personal relationships, community re-integration, return to sports, and the ability to work or go to school. Unfortunately, the pathophysiology of persistent concussive symptoms remains poorly understood, and very few treatment options are available.

After concussion, optimal cerebral blood flow is necessary to meet the metabolic needs of the injured brain. However, cerebral blood flow is diminished globally after injury, and in fact, there may be an inverse relation between regional flow and symptom burden after concussion. Thus, cerebrovascular dysfunction may play a role in the manifestation of prolonged concussive symptoms. Moreover, alterations in cerebral perfusion may act as a trigger in symptom exacerbation. Even if overt symptoms are mostly gone, strenuous effort may induce symptoms, presenting a major obstacle to return to daily activities. However, prolonged cessation from physical activity may also induce concussion-like symptoms, such as difficulty sleeping, concentration abnormalities, and anxiety.

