**Figure 1: Modified sub-maximal exercise protocol**

#### **(4) Definition of Primary and Secondary Outcomes/Endpoints**

- Primary: blood oxygenation level in the prefrontal cortex before and after the administration of the exercise protocol.
- Secondary: the proportion of participants who continue to experience symptoms after the 8-week exercise intervention and the potential confounding variables that contributes to this risk of persistent symptoms.

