***Schedule:***

Recruitment: Potential concussed subjects will be recruited from the sports medicine clinic at Boston Children's Hospital by a research staff member. If the subject is eligible and interested in participating they will schedule study visit 1 with the research staff member.

Study Visit 1 (time of enrollment):

Subjects will come to The Micheli Center for Sports Injury Prevention or Spaulding Hospital in Cambridge for a two hour visit. Once they give consent we can schedule a time for testing.

Subjects will be measured for height and weight. Subjects will complete a short medical history questionnaire, which includes the DHS, HADS, PHQ and a PCSI/ PSCC. Subjects will then be fitted for a Polar Wrist Unit and Heart Rate Monitor. During this time, they will also have a standard 5-lead ECG placed by a trained research member. Additionally, a research member will attach a blood pressure cuff to their non-dominant arm and to their middle finger (for photoplethysmographic measurements) and set up to the TCD and NIRS system. Both the usual care group and intervention group will complete this part of the study.

The first part of the study procedure involves supine rest, performing mental tasks, CO2 rebreathing, and resistance breathing to induce small periodic oscillations in arterial pressure. For resistance breathing, volunteers will breathe through a mouthpiece attached to a standard impedance threshold device made from latex-free PVC (PowerBreathe) set-up to moderate breathing resistance (10-20 cmH2O). There are no risks associated with mental or physical tasks (N-Back and finger tapping tasks) or resistance breathing. The CO2 re-breathing may cause slight lightheadedness in some people; however, this can be reversed almost immediately by switching them back to room air. Both usual care and intervention groups will complete this part of the study.

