The second part of the procedure involves the branching graded exercise test. Subjects will still be monitored using a standard 5-lead ECG and blood pressure measured by oscillometric blood pressure cuff. Throughout the graded exercise test cerebral blood flow will be monitored via TCD or NIRS. The subjects will also be connected to the metabolic cart to measure VO2. The exercise test will continue until the subject reports an increase in symptoms, using the abbreviated concussion symptom inventory or to 85% of their age-predicted maximum heart rate determined by the 5-lead ECG. The subject will be taken off the bike and cool down. Measurements will be taken for an additional five minutes. Both the usual care and intervention group will complete this part of the study.

After completion of testing, the subject will have the ECG, blood pressure cuff, metabolic cart, TCD and NIRS system removed. They will be monitored by a trained professional until symptoms ease or subject's heart rate and blood pressure has returned to resting values.

The final part of the procedure includes the single/ dual-task gait evaluation and VOMS.

Weeks 1-4 (at-home exercise):

Subjects in the intervention group will be advised to participate in aerobic exercise five days a week. This includes walking, biking, jogging and running. While participating in these activities, they will be wearing their Polar Wrist Unit and Heart Rate Monitor to help subjects track their exercise intensity. They will exercise for 20 minutes five times a week at 80% of their heart rate reverse, determined by their resting heart rate and maximum heart rate reached during exercise testing.

Usual care subjects will follow their physician's instructions for exercise and rest. They will also wear the Polar Wrist Unit and Heart Rate Monitor to track their exercise intensity, but will not receive a heart rate specific exercise recommendation.

Study Visit 2 (approximately 4 weeks post-enrollment):

All participants will participate in this visit. Subjects will undergo the same procedures as visit one, including the DHS, HADS, PHQ, PCSI/ PCSS, supine rest, graded exercise test, VOMS and

single/dual- task gait. At this time, the target heart rate for exercise will be adjusted to a new symptom limited heart rate for all participants who are still symptomatic based on the same procedure.

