### **(6) Study Timeline (as applicable)**

Once IRB approval is given we will start the recruitment process. We plan to enroll and complete testing for a total of 60 subjects over the next year.

Timeline for all subjects:

- Recruited from Boston Children's Hospital Sports Medicine clinic
- Comes in within 14 days of injury for study 1 visit
- Comes in 4 weeks later for study 2 visit
- Comes in 4 weeks later for study 3 visit

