## **H. Data Analysis Plan**

This protocol seeks to elucidate the relationship between regional brain blood flow and CO2 during exercise in individuals who have experienced a mild TBI, and to assess the effect of a standardized exercise protocol on cerebral blood flow.

Total hemoglobin concentration in the pre-frontal cortex will be calculated as the sum of oxygenated and deoxygenated hemoglobin (as measured by NIRS) and will serve as a surrogate for regional cerebral blood flow. The brain blood flow and end-tidal CO2 data will be aligned in time. The linear relationship between the two time series will be determined and compared across injury duration and symptom severity. We will use a linear mixed effect model akin to a multiple linear regression model where regional cerebral blood flow is used as the dependent variable, end-tidal CO2 is the independent variable, and symptom duration and amount of exercise are covariates.

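### The only symptom endpoint is read at week 8, well after the protocol expects most patients to have recovered, so an effect of exercise on the speed of recovery would be largely missed

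*Combined protocol and SAP*

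**What the plan says.** Section D(4) lists two outcomes. The first is not a symptom measure: "Primary: blood oxygenation level in the prefrontal cortex before and after the administration of the exercise protocol". The second is the only symptom endpoint: "the proportion of participants who continue to experience symptoms after the 8-week exercise intervention", together with the variables that may contribute to persistence.

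On timing, section D(6) gives "Comes in within 14 days of injury for study 1 visit". The next visit is "Study Visit 2 (approximately 4 weeks post-enrollment", and Visit 3 is at 8 weeks. Section B states "Recovery of symptoms following a concussion usually occurs within a few days to a few weeks of injury".

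Symptom scales are named at each visit. The Visit 1 questionnaire is one "which includes the DHS, HADS, PHQ and a PCSI/ PSCC". At Visit 2, "Subjects will undergo the same procedures as visit one, including the DHS, HADS, PHQ, PCSI/ PCSS, supine rest" and further tests are listed, and Visit 3 repeats the scales. Section D(3) says that symptoms will be monitored with four instruments but adds no other frequency. Between visits the documents describe heart-rate monitoring and exercise logs, and no symptom record.

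**The concern.** Aim 2 asks whether exercise affects concussion symptoms, and section B argues that early exercise may help symptoms resolve. An effect of that kind shows mainly in how soon patients recover. Visit 2 falls about 4 to 6 weeks after injury and Visit 3 about 8 to 10 weeks. By the protocol's own account, usual recovery therefore falls largely between Visits 1 and 2, where nothing is recorded, and the endpoint is read four weeks later still. A real gain in speed could have mostly faded by then. The search for variables linked to persistence would also rest on few events. Resolution dates that are not recorded during follow-up are hard to recover afterwards.

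**Working it through.** **Plan's own figure.** There is none for symptoms. The only power statement (section I) concerns the relation of blood flow to CO2, and no persistence rate, symptom threshold or dropout rate is given.

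**Inputs from the documents.** Up to 60 patients randomised equally (D(1)), so 30 per arm; p-value cutoff 0.05 (section I), taken here as two-sided; visits at weeks 0, 4 and 8.

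**Assumptions.** Exponential recovery from enrolment; all 60 symptomatic at Visit 1; no dropout; usual-care median m of 14, 21 or 28 days, to span section B's wording; recovery-rate ratio (HR) of 2 or 1.5.

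**Formulas.**
- Proportion still symptomatic at day t: 0.5^(t/m) in usual care and 0.5^(t × HR/m) with exercise.
- Single-time comparison: exact Fisher power, enumerating all outcomes with 30 per arm.
- Time to resolution: power = Φ(ln HR × √(E/4) − 1.96), where E is the expected number of resolutions by day 56.

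**Unobserved recovery.** By day 28, 1 − 0.5^(28/m) of usual-care patients have resolved: 75%, 60% and 50% for m = 14, 21 and 28.

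**Worked case, m = 21, HR 2.** Week 8: usual care 0.5^(56/21) = 15.7% (4.7 of 30); exercise 0.5^(112/21) = 2.5% (0.7 of 30). Fisher power is 19%. Then E = 60 − 4.7 − 0.7 = 54.5 before rounding, and Φ(0.693 × √(54.5/4) − 1.96) = Φ(0.60) = 73%.

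| HR | Median m (days) | Week 8, usual care v exercise | Fisher, week 8 | Fisher, week 4 | Log-rank to week 8 |
|---|---|---|---|---|---|
| 2 | 14 | 6.3% v 0.4% | 1% | 37% | 75% |
| 2 | 21 | 15.7% v 2.5% | 19% | 45% | 73% |
| 2 | 28 | 25% v 6.3% | 37% | 41% | 69% |
| 1.5 | 14 | 6.3% v 1.6% | 1% | 14% | 34% |
| 1.5 | 21 | 15.7% v 6.3% | 8% | 15% | 32% |
| 1.5 | 28 | 25% v 12.5% | 14% | 14% | 29% |

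At HR 2, the number still symptomatic at week 8 in both arms together is about 2, 5.5 and 9.4 of 60.

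**Sensitivity.**
- Fisher's test is conservative with few events. A normal approximation at HR 2 gives 24%, 43% and 52% at week 8, still below log-rank.
- Slower recovery narrows the gap: at m = 42 and HR 2, week-8 Fisher power is 45% against 63% for log-rank.
- Without any recovery model, halving the week-8 proportion stays below 80% power for every usual-care rate tried from 5% to 50%. At 20% v 10%, Fisher power is 10%, and about 199 per arm would be needed (normal approximation). With 0 of 30 in one arm, the other needs at least 6 of 30 for Fisher p < 0.05.
- At HR 2, 80% log-rank power needs 66 resolutions, more than the 60 patients planned.

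**How much needs new data.** In simulation at HR 2, log-rank on the existing 4-week visit grid gives roughly 60% to 68%, against roughly 68% to 73% with weekly recording. Most of the gain comes from using Visit 2.

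**The case against.** The strongest defence is that persistence is a stated target. Section B speaks of reducing the risk of persistent symptoms, and D(4) names that risk, so a reading at the end of the intervention answers a legitimate question. That stands, and is why the week-8 proportion should stay. It does not cover the effect on recovery speed that Aim 2 also includes.

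The number still symptomatic at week 8 is also unknown. Section B says only what usually happens, and patients come largely from a hospital sports medicine clinic, where recovery may be slower. That stands as a limit on the size of the problem, which is why a range is shown.

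The alternative has limits too. Its figures assume that everyone is symptomatic at entry, which the inclusion criteria do not require, and that resolution is dated exactly. If 80% of patients contribute, the m = 21, HR 2 figure falls from 73% to about 63%. Weekly self-report in a non-blinded trial is open to expectation effects.

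Three stronger readings are tempting but unsupported:
- A reader might infer that both arms would be near zero at week 8 even if exercise cut median recovery from 3 weeks to 2. Under the model above that is HR 1.5 and leaves 16% v 6%, about 4.7 v 1.9 of 30. Log-rank power there is only 32%, so the added analysis would probably miss that effect as well.
- A reader might infer that the trial is bound to report no effect. Week-8 power is low but reaches 37% in one case.
- A reader might infer that section H, where "symptom duration and amount of exercise are covariates", must have a resolution date. The term can equally mean how long symptoms have lasted at the time of each test.

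**Conclusion.** The point holds as a mismatch between when symptoms are read and when the protocol expects them to resolve. For a doubled recovery rate, week-8 Fisher power is 1% to 37% over usual-care medians of 14 to 28 days, against 69% to 75% for time to resolution. For a rate ratio of 1.5 it is 1% to 14% against 29% to 34%. These figures rest on the assumed exponential recovery, full symptomatic enrolment and no dropout. The ordering is firmer than the individual values. The change is an improvement, but it does not bring the symptom comparison to 80% power. The endpoint is secondary and no power is claimed for it, so this is a worthwhile correction rather than a fatal flaw.

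**What to change.** Keep the week-8 proportion in D(4) as the persistence endpoint. Add a comparison between randomised arms of time to symptom resolution, among participants symptomatic at Visit 1, and report the Visit 2 proportion beside it. State what score counts as resolved, since D(4) gives no threshold.

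- **Minimum.** Use the Visit 1 to 3 scores already scheduled, with an interval-censored or discrete-time analysis. This costs protocol and analysis wording only.
- **Preferred.** Also send the abbreviated CSI, already a trial instrument, weekly through the existing REDCap survey from Visit 1 until resolution or week 8, and record the resolution date.

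The weekly survey adds a slight burden for participants, some staff time to follow up missed surveys, and further unblinded self-report. Neither version needs extra visits or patients. Report the symptom comparison with its confidence interval, and say that it is not powered at 80%.

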## **D. Design and Methods**

### **(1) Study Design**

Prospective, non-blinded, Interventional study

We plan to recruit up to 60 concussed patients, equally randomized to an intervention group who participate in the at home exercise program, or those who undergo the same testing but receive the standard of care given by their physician. Subjects will be recruited from Boston Children's Hospital Sports Medicine Clinic, The Micheli Center for Sports Injury Prevention as well as affiliated schools, clinics and sports organizations. The subjects and parents/guardians who voluntarily agree to participate will be scheduled for three visits. Upon the first visit, a research coordinator will explain the study and have the subject and parent/guardian sign the "Research Consent Form", approved by the Institutional Review Board of Boston Children's Hospital before participating in the study. Subjects will be required to complete three visits to The Micheli Center for Sports Injury Prevention or Spaulding Hospital in Cambridge for testing.

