## **(3) Description of Study Treatments or Exposures/Predictors**

Concussion Symptoms will be monitored by the Post-Concussion Symptom Inventory (PCSI), Post-Concussion Symptom Score (PCSS), the abbreviated Concussion Symptom Inventory (CSI), and Visual analog scale (VAS)

Surveys: Dizziness Handicap Scale, Hospital Anxiety and Depression Scale (HADS), Patient Health Questionnaire (PHQ) will be completed before each testing visit.

Height and weight will be measured.

Heart rate, cerebral blood flow, and end-tidal CO2 will be recorded during a one hour session, before graded exercise test, during a graded exercise test on a cycle ergometer, and during 5 minutes of recovery. The branching exercise protocol (shown in Figure 1 below) based on the modified YMCA protocol will progressively increase exercise intensity up to 85% of age-predicted maximum heart rate. Exercise will be stopped at this point or if the volunteer becomes symptomatic.

Single/ Dual-Task Gait: Patients will be instrumented with three accelerometer devices, attached via elastic strap at L5, left, and right feet, which take less than one minute to place on the patient. The devices will be wirelessly connected to a laptop run by the study coordinator to obtain and save motion data. While wearing these devices, they will complete tasks in three different conditions:

- *Standing single-task:* patients will be seated and be asked to complete a mini-mental status examination, adapted from previous investigations and recommendations. It consists of spelling a five letter word backwards, serial subtraction of 6s or 7s, or reciting the months in reverse order. 8 trials will be completed.
- *Walking single-task:* patients will be instructed to walk down the hall at a length of 10m, turn around and return to the original starting point, with no obstruction or completion of other tasks. 8 trials will be completed.
- *Walking dual-task:* patients will be instructed to walk down the hall at a length of 10m, turn around and return to the original starting point, while completing a mental status examination. The examiner will ask the patient to spell a five letter word backwards, subtract by 6s or 7s from a number, or recite the months in reverse order. The examiner will say, "Ready, go" and the patient will begin walking while completing the mental task. 8 trials will be completed.

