#### Study Visit 3 (8 weeks post-enrollment):

All subjects will participate in this visit (usual care and intervention). Subjects will undergo the same procedures as visit one, including completing the DHS, HADS, PHQ, PCSI/PCSS, cerebrovascular function tests, graded exercise test, VOMS and single/ dual-task gait.

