### **F. Data Management Methods**

Medical health information will be saved and input using RedCap survey. There will be an internal RedCap to enter recruitment information and identifying information. It will also include the exercise logs to help blind the PI from knowing which intervention group the subjects are in. The external RedCap will include the surveys, concussion history and test measurements. The information will be stored using the study ID numbers consistent with the rest of the measurements. Data from the heart rate monitors will be securely transferred from the device to a BCH-encrypted computer via USB drive.

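### Week-8 symptom status can be obtained only by attending Visit 3, so a missed visit loses the outcome and could bias the arm comparison in either direction

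*Combined protocol and SAP*

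**What the plan says.** Section D(4) gives the secondary endpoint as "the proportion of participants who continue to experience symptoms after the 8-week exercise intervention". It names no denominator, no analysis set and no rule for a participant whose status is unknown.

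Section D(1) says "Subjects will be required to complete three visits". In the D(5) schedule the PCSI/PCSS appears at Visits 1, 2 and 3 and nowhere between them. Visit 1 is planned as two hours, and the later visits repeat its procedures. For Visit 3 the text reads "All subjects will participate in this visit (usual care and intervention", and the procedures are listed as "including completing the DHS, HADS, PHQ, PCSI/PCSS, cerebrovascular function tests, graded exercise test", followed by the vestibular and gait tests. The entry for weeks 4 to 8 covers only activity and heart-rate monitoring.

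Section D(3) says that the dizziness, anxiety/depression and patient health surveys "will be completed before each testing visit". Section F says "The external RedCap will include the surveys, concussion history and test measurements".

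On numbers, D(1) says "We plan to recruit up to 60 concussed patients, equally randomized to an intervention group", which is 30 per arm at full recruitment. D(6) says "We plan to enroll and complete testing for a total of 60 subjects over the next year", so no loss is allowed for. Section H does not analyse the symptom proportion, and Section I sizes the trial on the relation between blood flow and CO2. The text between Sections I and K was not available for this review.

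**The concern.** The symptom proportion is the only listed endpoint that is a clinical outcome. Comparing it between arms needs a week-8 status for each person randomised, but the plan obtains that status only from those who come to a laboratory visit that includes an exercise test. A score not collected at week 8 cannot be recovered later.

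The plan itself suggests why absence might not be random. Section B says that recovery usually takes days to weeks, so many participants may be well by week 8 and see little reason to return. Section E accepts that exercise may trigger symptoms, which gives symptomatic participants a reason to avoid the test. Participants know their arm, and only the intervention arm is asked to exercise 20 minutes five times a week. If attendance depends on symptoms, and does so differently in the two arms, the proportions among attenders will differ even where the true proportions are equal.

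**Working it through.** The documents give no figure for this endpoint to reproduce: no expected proportion, no loss rate and no power. The R² of 0.31 in Section I concerns a different question and has no bearing here. Every rate below is an assumption.

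**Formula.** Let *p* be the true week-8 proportion symptomatic, *s* the fraction of symptomatic participants who miss Visit 3, and *r* the fraction of recovered participants who miss it. Then

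observed proportion = p(1 − s) / [p(1 − s) + (1 − p)(1 − r)]

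overall loss = p·s + (1 − p)·r

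**Opposite patterns, p = 0.30 in both arms.**
- Exercise, s = 0.30, r = 0.05: 0.210 / (0.210 + 0.665) = 0.210/0.875 = 24.0%; loss 12.5%.
- Usual care, s = 0.05, r = 0.20: 0.285 / (0.285 + 0.560) = 0.285/0.845 = 33.7%; loss 15.5%.
- False difference: 9.7 points in favour of exercise. Swapping the patterns between arms gives 9.7 points against it. The losses are 0.125 × 30 = 3.75 and 0.155 × 30 = 4.65, about four or five people per arm.

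**Varying the assumptions.** Usual care keeps s = 0.05, r = 0.20, except in the last row.

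| True p, both arms | Exercise s, r | Exercise observed | Usual care observed | False difference |
|---|---|---|---|---|
| 0.20 | 0.30, 0.05 | 15.6% | 22.9% | 7.3 points |
| 0.40 | 0.30, 0.05 | 32.9% | 44.2% | 11.2 points |
| 0.30 | 0.30, 0.20 | 0.210/0.770 = 27.3% | 33.7% | about 6 points |
| 0.30 | 0.15, 0.20 | 0.255/0.815 = 31.3% | 33.7% | about 2 points |
| 0.30 | 0.30, 0.05 (both arms) | 24.0% | 24.0% | 0 |

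The result depends far more on how the loss patterns differ between arms than on the true proportion.

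**Bounds that assume nothing about why people are missing.** With *m* of 30 missing in each arm, the best-to-worst-case range for the arm difference is 2m/30 wide: 20 points for m = 3, 40 for m = 6, 60 for m = 9.

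**Which sensitivity analysis works.** Take the opposite-patterns example at p = 0.30, where the true difference is zero, and use all randomised as the denominator.
- All missing counted as symptomatic: 0.210 + 0.125 = 33.5% v 0.285 + 0.155 = 44.0%, a false 10.5 points.
- All missing counted as recovered: 21.0% v 28.5%, a false 7.5 points.
- Missing symptomatic in exercise, recovered in usual care: 33.5% v 28.5%, a difference (exercise minus usual care) of +5.0 points.
- The reverse: 21.0% v 44.0%, −23.0 points.

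Applying the same assumption in both arms misses the true zero in both versions. The opposite assumptions bracket it.

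**The case against.** The strongest reply is that the plan already intends full follow-up. Visit 3 is for everyone in both arms, no section withdraws a participant who stops exercising, and Section H uses amount of exercise as a covariate, so uneven adherence is expected. A reader might infer that those who stop exercising fall out of the symptom proportion, or that the endpoint counts only those who finished the programme. The documents support neither inference. The D(4) wording refers to participants, and its mention of eight weeks most naturally marks a time. The requirement to complete three visits describes the commitment and is not a withdrawal rule. This part of the reply stands. What it leaves open is what happens when someone does not attend.

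The second reply is that bias is conjectural. The documents give no loss or symptom rates. Symptomatic participants may value follow-up, and recovered participants may stay away equally in both arms. With about 30 per arm, the standard error of the difference at 30% is √(2 × 0.3 × 0.7/30) = 0.118, about 12 points, larger than the illustrated bias. This too stands as a limit on what can be claimed about size and direction. It does not supply the missing outcome.

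Third, off-site completion is left unspecified but is not ruled out: some surveys are to be done ahead of the visit, and RedCap is in use. That is fair, and it is why the remedy is easy. Finally, the plan names neither the scale nor the cut-off that defines a symptomatic participant, and it does not analyse the proportion. Those are separate gaps that better follow-up does not close.

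**Conclusion.** The point holds in limited form. On the available text, week-8 symptom status depends on attending Visit 3, and no other route or missing-data rule is given. Loss could depend on symptoms and arm, and the resulting bias could favour either arm. With a true 30% in both arms, the false difference is zero if the loss patterns match, about 2 to 6 points under intermediate assumptions, and about 10 points if the patterns are opposite. A reader might take the 10 points as an expected false benefit of exercise. The documents do not support that, because the figure rests on loss rates chosen to be opposite in the two arms. This is a cheap improvement to a secondary endpoint. It does not show that the comparison will be biased.

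**What to change.** - **D(5):** state that PCSI/PCSS at weeks 4 and 8 is obtained from every randomised participant, by the existing RedCap survey (link or phone) if the visit is missed, and whether or not the participant is still exercising. Record the reason for each missed visit, by arm.
- **D(4):** word the endpoint as symptomatic at 8 weeks after enrolment, among all randomised participants by assigned arm.
- **Section H:** where status is still unknown, report best- and worst-case bounds with opposite assumptions in the two arms (missing counted as symptomatic in one and recovered in the other, then reversed), not the same assumption in both.

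The cost is protocol wording plus a survey link or short call for those who miss a visit. No new instrument or procedure is needed. The downside is that a few scores will be completed remotely rather than on site.
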